6.3.2. Exclusion criteria for Subject Selection

1. Patients with a severe Dry Eye condition (severity level 4 according to the Report of the International Dry Eye Workshop -DEWS, 2007)
2. Best corrected distance visual acuity (BCDVA) score of < 0.1 decimal units in either eye at the time of study enrolment
3. Evidence of an active ocular infection in either eye
4. History or presence of ocular surface disorders other than ocular discomfort in either eye
5. Use of any ocular topical medication other than the study medications for the treatment of ocular diseases including artificial tears during the study period
6. Use of topical cyclosporine, topical corticosteroids or any other topical medication for the treatment of dry eye in either eye within 30 days of study enrolment
7. History of any ocular surgery (excluding laser or refractive surgical procedures) in either eye within 30 days before study enrolment. Ocular surgery will not be allowed during the study treatment period and elective ocular surgery procedures should not be planned during the duration of the follow-up period
8. Known hypersensitivity to one of the components of the study or procedural medications
9. Participation in another clinical study at the same time as the present study or within 90 days of screening/baseline visit
10. History of drug, medication or alcohol abuse or addiction.
11. Females of childbearing potential (those who are not surgically sterilized or post-menopausal for at least 1 year) are excluded from participation in the study if they meet any one of the following conditions:
 - a. are currently pregnant or,
 - b. have a positive result on the urine pregnancy test at the Screening/Baseline Visit or,
 - c. intend to become pregnant during the study treatment period or,
 - d. are breast-feeding or, not willing to use highly effective birth control measures, such as: Hormonal contraceptives – oral, implanted, transdermal, or injected and/or mechanical barrier methods – spermicide in conjunction with a barrier such as a condom or diaphragm or IUD during the entire course of and 30 days after the study treatment periods.

6.3.3. Criteria and Procedure for Subject Withdrawal or Discontinuation

A subject should be withdrawn from the trial if, in the opinion of the Investigator, it is medically necessary or if it is the wish of the subject.

The study treatment will be discontinued at any time if any of the following events occur:

- **Adverse event:** Any significant adverse event that in the opinion of the investigator or concerned subject is not compatible with study continuation. For the definition of AE, please refer to [§ 14](#).
- **death:** the absence of life or state of being dead
- **lost to follow-up:** the loss or lack of continuation of a patient to follow-up
- **non-compliance with study ID:** an indication that a patient has not agreed with or followed the instructions related to the study medication
- **physician decision:** a position, opinion or judgment reached after consideration by a physician with reference to the subject

- **pregnancy:** pregnancy is the state or condition of having a developing embryo or fetus in the body (uterus), after union of an ovum and spermatozoon, during the period from conception to birth
- **protocol deviation:** an event or decision that stands in contrast to the guidelines set out by the protocol
- **study terminated by Sponsor:** an indication that a clinical study was stopped by its Sponsor
- **site terminated by Sponsor:** an indication that a clinical site was stopped by the study Sponsor
- **technical problems:** a problem with some technical aspect of a clinical study, usually related to an instrument
- **withdrawal by subject:** study discontinuation requested by a subject for whatever reason
- **other:** different than the ones previously specified

Any treatment discontinuation must be recorded on the case report form (CRF) by the Investigator, who will indicate date and reason(s) for treatment withdrawal. Unless the subject has withdrawn consent, the early termination visit assessments should be performed as detailed in Section 6.1.3.

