6.2. ID AND COMPARATORS

6.2.1. Description and Justification of ID/Comparator Exposure

During the 2 week (15±2 days) double-masked, randomized, controlled treatment period, (hereafter, also referred to as the controlled treatment period) enrolled subjects will be randomized at baseline in a 1:1:1 ratio to the experimental treatment arm (Lubricin 20 µg/ml or Lubricin 50µg/ml, one drop TID for two weeks) or the control arm Vismed® 0.18% (sodium hyaluronate eye drop solution, one drop TID for two weeks).

During the follow-up period at the discretion of the treating physician any ocular topical treatment is allowed, including other artificial tears/lubricants.

Investigational Medical Devices will be administered by ocular route according to 1:1:1 randomization. If the subject forgets to take the study drug, it should be taken as soon as the subject remembers.

The proposed duration of the treatment has been considered as adequate to support local tolerability, safety and efficacy of the product in comparison with the selected control.

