11.3 Control of Occurred Treatment

The investigator/s will ensure that the subject has received the Test ID/Control ID at Visit 1; any deviations from the fixed dosing will be specifically asked to the subjects at each visit and deviations will be included in the CRF. The Investigator should accurately complete all the ID Accountability Forms at all visits and check treatment self-administration compliance.

Any new information about the IDs will be communicated to the subject and the consent modified and submitted to the EC for approval.

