16.1.1 Removing Subjects from the Study

A subject should be withdrawn from the trial if, in the opinion of the Investigator, it is medically necessary or if it is the wish of the subject.

The study treatment will be discontinued at any time if any of the following events occur:

- Development of AE or unacceptable toxicity, precluding further therapy with the IDs. Severe protocol violations, such as an incorrect treatment administration, or a concomitant use of not permitted medications. Before removal, these cases should first be discussed with Dompé farmaceutici s.p.a.
- Severe protocol violations, such as an incorrect treatment administration, or a concomitant use of not permitted medications. Before removal, these cases should first be discussed with Dompé farmaceutici s.p.a.
- Subject request.
- Subject has been enrolled, but has not started study treatment e.g. due to onset of AE, consent withdrawal etc before treatment could be started.
- Subject becomes pregnant
- Treating physician decision in the subject's best interest.
- Onset of ocular conditions requiring additional topical treatments (e.g. onset of ocular inflammation, infection, hypertension etc) or surgery
- Request of Dompé farmaceutici s.p.a.

Any treatment discontinuation must be recorded on the case report form (CRF) by the Investigator, who will indicate date and reason(s) for treatment withdrawal. Unless the subject has withdrawn consent, the early termination visit assessments should be performed as detailed in [§ 6.1.3](#).

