8.7.5 Protocol deviations

All the protocol deviations reported during the clinical investigation will be listed ([Listing 16.2.2.1](#)) and summarised by treatment. The number and proportion of subjects for each deviation will be reported ([Table 14.1.1.5](#)).

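### Protocol 6.3.3 puts the CRF discontinuation reason codes under a mandatory stopping sentence, which contradicts 16.1.1 and 16.1 on minor deviations

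*Protocol*

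**What the plan says.** Protocol 6.3.3, on criteria and procedure for withdrawal, states: "The study treatment will be discontinued at any time if any of the following events occur". Twelve items follow. Three of them are defined without any degree of severity:

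- protocol deviation: "an event or decision that stands in contrast to the guidelines set out by the protocol";
- non-compliance with the device: "an indication that a patient has not agreed with or followed the instructions related to the study medication";
- technical problems: "a problem with some technical aspect of a clinical study, usually related to an instrument".

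A fourth, 'other', covers anything not already named. The adverse-event item does limit itself, to significant events judged incompatible with continuing.

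Section 16.1.2.1 repeats the 12 items under the title of primary reason for discontinuation. Sections 16.1.3 and 16.1.4 have the primary reason recorded when a subject discontinues.

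Section 16.1.1 starts with the same sentence as 6.3.3 but has a different list. Its entry for violations is "Severe protocol violations, such as an incorrect treatment administration, or a concomitant use of not permitted medications", and such cases should be discussed with the sponsor before removal. It has no entry for technical problems or 'other'. Section 16.1 asks the investigator to make every reasonable attempt to retain a subject who has no relevant violation and no medical contraindication.

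On dosing, 6.2.1 says: "If the subject forgets to take the study drug, it should be taken as soon as the subject remembers".

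**The concern.** Sections 6.3.3 and 16.1.1 are both written as operative rules, and for a minor deviation they give opposite answers. Under 6.3.3 treatment stops. Under 16.1.1 it does not, because the violation is not severe, and 16.1 adds a duty to keep the subject. Whichever the investigator chooses, one section is breached, and no text gives an order of precedence.

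What is at stake is first whether a subject goes on receiving treatment, and second the data. Discontinued subjects are not replaced (Protocol 6.1.5), arms have 10 subjects (6.3.7), and missing values are not imputed (SAP 8.5). A subject who is stopped goes to the early termination visit, so a stop before Visit 2 means that no on-treatment Day 15 assessment is made.

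**Working it through.** **Comparing the sections for a minor protocol deviation**

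| Section | Trigger | Consequence |
|---|---|---|
| 6.3.3 | any deviation | treatment stops; no prior discussion mentioned |
| 16.1.1 | severe violation only | treatment stops, after discussion with the sponsor |
| 16.1 | no relevant violation or medical contraindication | reasonable efforts to retain |

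The first row contradicts the other two. The contradiction is confined to minor, non-relevant deviations. A severe violation stops treatment under both 6.3.3 and 16.1.1.

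**The SAP's own figure**

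Inputs (SAP 8.4.1): σ = 10 mm, ω = 9 mm, two-sided α = 0.05, z = 1.960.

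n per arm = ceiling(2σ²z²/ω²) = ceiling(2 × 100 × 3.8415 / 81) = ceiling(9.485) = 10. This reproduces the stated 10.

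**Effect of losing one subject's Day 15 VAS**

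Half-width = 1.960 × 10 × √(1/n₁ + 1/n₂).

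| Arms compared | Half-width |
|---|---|
| 10 v 10 | 8.77 mm |
| 9 v 10 | 9.01 mm |
| 9 v 9 (after the 10% drop-out expected in Protocol 7.3) | 9.24 mm |
| 8 v 9 | 9.52 mm |

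The relative widening does not depend on σ. It is √[(1/9 + 1/10)/(2/10)] = 1.027 for the first loss, and √[(1/8 + 1/9)/(2/9)] = 1.031 after the expected drop-out.

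**What is lost, by time of stopping**

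Scheduled VAS time points: 3 at Visit 1, 3 at Visit 2 and 1 at Visit 3, total 7.

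- *Stop on Day 1 after the post-dose measurements.* Loses 3 + 1 = 4 and gains 1 at the early termination visit, a net loss of 3 of 7 (43%). The subject also leaves all 8 Day 15 comparisons in SAP 8.11.4.1 to 8.11.4.8 (7 t tests and 1 Wilcoxon section). The VAS repeated-measures model could still use the values that remain.
- *Stop at Visit 2 after the pre-dose assessments.* Loses 2 + 1 = 3 and gains 1, a net loss of 2 of 7 (29%). None of the 8 comparisons is affected. The Day 15 post-dose tear samples are lost, but SAP 8.10 only lists the concentrations.

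**When a deviation would be noticed**

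The flow chart has no contact between Day 1 and Visit 2, and Protocol 11.3 has dosing deviations asked about at visits. Most home-dosing deviations would therefore surface at Visit 2, which is the second and cheaper case. The first case needs a minor deviation seen earlier, for illustration a mistimed post-dose sample on Day 1.

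**The case against.** The strongest reply is that nobody would apply 6.3.3 literally. Death and loss to follow-up cannot work as instructions to stop. 'Physician decision', read the same way, would make any medical opinion about the subject end treatment. The list is visibly a set of reason definitions, as 16.1.2.1 confirms. For minor deviations, 16.1.1 and 16.1 already give the more specific guidance. The SAP calls the study exploratory, with no regulatory claim (8.3), and says that its VAS assumptions rest on no clinical or literature data (8.4), so little hangs on a fraction of a millimetre.

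Most of this stands, and it sets the size of the point. It does not remove the contradiction. The same sentence is plainly binding in 16.1.1, and a site has no textual ground for treating it as a label in 6.3.3.

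A reader might infer a wider conflict, which the documents do not support:

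- *Section 6.2.1.* It might seem that one forgotten dose must end treatment: three doses a day for 14 days is 42, so one dose is 2.4%. But a subject who takes a forgotten dose late is doing what 6.2.1 says, and can fairly be described as following instructions. A dose missed altogether is a different case, which 6.2.1 does not address. This is a supporting tension only.
- *Section 11.3 and SAP 8.7.5.* The first provides that "any deviations from the fixed dosing will be specifically asked to the subjects at each visit and deviations will be included in the CRF". The second says: "The number and proportion of subjects for each deviation will be reported". Recording and tabulating deviations is needed whether or not treatment stops, so neither conflicts with 6.3.3.

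**Conclusion.** The contradiction between 6.3.3 and sections 16.1.1 and 16.1 is real and rests on the text alone. It is a minor consistency correction to an operative rule.

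The likely practical effect is small. How often 6.3.3 would be applied literally cannot be known from the documents, and the surrounding sections make it unlikely. Only a stop before Visit 2 costs a subject's on-treatment Day 15 data. One such loss widens the VAS half-width by about 3%, from 8.77 to 9.01 mm against the 9 mm target, or from 9.24 to 9.52 mm after the expected drop-out. The millimetre figures assume the SAP's SD of 10 mm. The Visit 2 case assumes that the stop follows the pre-dose assessments.

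A reader might conclude that the wording threatens the trial's precision or its analysis. The documents do not support that. They give no rate of minor deviations, and the expected 10% drop-out alone moves the half-width further (8.77 to 9.24 mm) than one additional stopped subject does.

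**What to change.** In 6.3.3, replace the lead sentence with *Reasons for discontinuation to be recorded in the CRF are:* and refer to 16.1.1 for the subject-level events that require treatment to stop. Leave the provisions on study termination (6.3.5, 16.1.2) and on envelope opening (16.2) as they are. If repeated non-compliance is meant to end treatment, add it to 16.1.1 with a stated threshold.

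This changes one sentence and adds one cross-reference. Visits, CRF, sample size and SAP are untouched. The downside is a wording amendment, which section 9 requires to be sent to the ethics committee and the competent authorities.

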6.3.4. Point of Enrolment

Subjects will receive the randomization number before enter in a 2 week double-masked, randomized, controlled treatment period, followed by 1 week follow-up.

6.3.5. Total Expected Duration of the Clinical Investigation

The study is expected to be completed within 3-4 months.

The study will be considered completed at the date of the last visit of the last subject or upon completion of any follow-up procedure described in the CIP. The investigator and the Sponsor have the right to discontinue the study at any time for reasonable medical and/or administrative reasons. As far as possible, this should occur after mutual consultation. Reasons for discontinuation have to be documented appropriately. In this event, no further subjects will receive doses of the IDs, and subjects already having received a dose of IDs will not receive any further doses of the study ID but will undergo all safety assessments scheduled after the last dose of ID, up to and including the end of study examination

6.3.6. Expected Duration for Each Subject

Treatment duration 14 days (2 weeks) \pm 2 days (maximum total study duration 16 days) and 1 week (7 ± 2 days) of follow-up.

The total maximum duration is expected to be about 25 days.

6.3.7. Total Number of Randomized Subjects

30 subjects (10 per arm) will be randomized to 1:1:1 ratio.

Recruitment will proceed until the planned number of randomized subjects is achieved.

6.3.8. Total Enrolment Time

The best total enrolment time is estimated to be of 45 days.

6.4. PROCEDURES

6.4.1. Clinical Investigation Procedures

6.4.1.1. Efficacy

Ocular Evaluations

Ocular evaluations will be performed on both eyes. The assessments must always be performed according the sequence (1 – 10) detailed in § 6.1.3. The assessment will be performed at visit 1 (day 1), 2 (day 15±2), 3 (day 22±2) /early termination visit.

The ophthalmological assessment will include:

1. ***Symptom Assessment in Dry Eye (SANDE)***: Subjects with SANDE overall score ≥ 30 mm are eligible for enrolment.

The SANDE questionnaire is a short questionnaire to evaluate both dry eye intensity and frequency by using a 100 mm VAS. The subject symptoms of ocular dryness and/or irritation will be quantified on the scale based on two questions that assess both severity and frequency of symptoms. A VAS is a measurement instrument that tries to measure a characteristic or attitude that is believed to range across a continuum of values and cannot easily be directly measured. For example, the amount of irritation that a subject feels ranges across a continuum from none to an extreme amount of irritation. From the subject's perspective this spectrum appears continuous (i.e. their irritation does not take discrete jumps, as a categorization of none, mild, moderate and severe would suggest). It was to capture this idea of an underlying continuum that the VAS was devised.

For the assessment, the subjects mark on the 100 mm VAS line the point that they feel represents their perception of their current state. The VAS score is determined by measuring in millimetres from the left hand end of the line to the point that the subject marks. The SANDE scores will be then evaluated for the 2 questions severity (0-100) and frequency (0-100).

2. ***Best corrected distance visual acuity (BCDVA)***: Subjects with best corrected distance visual acuity (BCDVA) score of ≥ 0.1 decimal units in both eyes are eligible for enrolment. Refraction and visual acuity measurements will be performed for all subjects by trained vision examiners only. The name of the vision examiner should be documented in the subject's visual acuity (VA) worksheet (provided by the Sponsor) at each visit. Refraction should be conducted prior to visual acuity testing to obtain best-corrected vision as described below. Best-corrected visual acuity is measured at all trial visits using standard charts, lighting, and procedures. Best correction is determined by careful refraction at that visit according to the standard protocol for refraction as described below

Equipment: Refraction equipment required includes:

- Retroilluminated Light box and ETDRS 4 meter distance acuity chart set
- Trial lens frames
- Trial lens set with plus or minus cylinder lenses
- Jackson cross-cylinders of 0.25, 0.50, and 1.00 diopters
- Pinhole occluder
- Tissues or eye pads and tape
- A 1 meter rigid measuring stick

Visual acuity charts: Chart 1 is used for testing the visual acuity of the RIGHT eye; Chart 2 for testing the LEFT eye; and Chart R (or 3) for refraction only. Subjects should not be allowed to see any of the charts before the examination.

A distance of 4 meters is required between the subject's eyes and the visual acuity chart. With the box light off, not more than 15 foot-candles of light (161.4 Lux) should fall on the centre of the chart. To measure the amount of light, the room is set up for visual acuity testing, but with the box light off. The light meter is placed at the fourth line from the top of the chart, with its back against the chart and the reading is taken. If more than one line available for testing visual acuity, the visual acuity of an individual subject should be measured in the same line at each visit, if possible. If different lines are used to test visual acuity, they must each meet the same standards.

Retroilluminated ETDRS charts are used in this trial. The illuminator box will be either wall-mounted or mounted on a stand. The light box should be mounted at a height such that the top of the third row letter is 49 + 2 inches from the floor.

The visual acuity light box is equipped with two General Electric 20-watt fluorescent tubes and ballast. Each tube is partly covered by a 14-inch fenestrated sleeve, which is centered on the tube and open in the back. This serves as a "baffle" to produce even illumination over the testing chart. Because the illumination of fluorescent tubes diminishes by 5 percent during the first 100 hours and by another 5 percent during the next 2000 hours, new tubes should be kept on for 4 days (96 hours) continuously, and should be replaced once a year

A sticker should be placed on the back of the light box, indicating the date when the present tubes were installed. A spare set of burned in bulbs should be available on site.

Detailed instructions for VA assessment As a reminder, Charts 1, 2 and R (or 3) are used for testing the right eye, left eye, and refraction, respectively. Subjects should not see the charts until the test begins. The lens correction from the subjective refraction should be in the trial frame worn by the subject.

All eyes must be tested at 4 meters first, even if the refraction was performed at 1 metre. The subject should be seated comfortably directly in front of the chart so that the eyes remain at the 4 meter distance. Testing always begins with the right eye. The fellow eye should be occluded with a folded tissue or eye pad lightly taped over the eye behind the trial frame serves as an effective occluder that allows eccentric fixation without inadvertent use of the covered eye. After testing the right eye, occlusion of the right eye should be done BEFORE Chart 2 is put up for testing the left eye.

The subject is asked to read the letters slowly, approximately one letter per second. The subject should be told that only one chance is given to read each letter, but may change their mind before moving to the next letter. If the subject is unsure about the identity of the letter, then the subject should be encouraged to guess.

The subject should begin by reading the top line of the chart and continue reading every letter on each smaller line, from left to right on each line. The subject should be encouraged to continue reading even if making mistakes. Each letter read is counted. The examiner circles every correct letter read and totals each line and the whole column (0 if no letters are correct) on the provided VA worksheet. An X is put through letters read incorrectly. Letters, for which no guess was attempted, are not marked. When a subject reaches a level where he/she cannot guess, the examiner may stop the test, provided that the subject has made errors on previous guesses, which is a clear indication that the best visual acuity has been obtained.

When a subject cannot read at least 20 letters on the chart at 4 meters, the subject is tested at 1 meter. The distance from the subject to the chart should be measured again using the rigid one meter stick. The distance is measured from the outer canthus to the center of the fourth letter (right eye) or the second letter (left eye) of the third line of the chart. The spherical correction

in the trial frame should be changed by adding +0.75 to correct for the closer test distance. The subject may fixate eccentrically or turn or shake his/her head to improve visual acuity. Particular care should be taken to make sure the subject does not move forward when testing at 1 metre. The subject should be reminded to blink.

The examiner should not tell the subject if a letter was identified correctly. The patient may be encouraged by neutral comments, such as “good”, “next”, and “OK”.

The examiner should not stand close to the chart during testing. Attention should be focused on the patient and the VA worksheet. If the patient has difficulty locating the next line to read, the examiner may go up to the chart and point briefly to the next line to be read, but then must move away from the chart.

When 20 or more letters are read at 4 meters the visual acuity score for that eye is recorded as the number of letters correct at 4 meters plus 30 (refer to the VA worksheet). The patient gets credit for the 30 letters at 1 meter even though they did not have to read them. Otherwise, the visual acuity score is the number of letters read correctly at 1 meter plus the number, if any, read at 4 meters. If no letters are read correctly at either 4.0 meters or 1 meter, then the visual acuity score is recorded as “0”.

3. **Slit lamp examination (SLE):** The slit lamp examination must be performed before the instillation of any dilating or anesthetic eye drops or the fluorescein agent.

The subject will be seated at the slit lamp while being examined. Grading of the eyelids, lashes, conjunctiva, cornea, lens, iris and anterior chamber will be done according to the following scales:

Eyelid - Meibomian glands (evaluation of the central ten Meibomian gland openings in the mid-portion of the upper eyelid):

0 = None (none are plugged).

1 = Mild (1 to 2 glands are plugged).

2 = Moderate (3 to 4 glands are plugged).

3 = Severe (All glands are plugged).

Eyelid - Erythema

0 = None (normal).

1 = Mild (redness localized to a small region of the lid(s) margin OR skin).

2 = Moderate (redness of most or all lid margin OR skin).

3 = Severe (redness of most or all lid margin AND skin).

4 = Very severe (marked diffuse redness of both lid margin AND skin).

Eyelid - Oedema

0 = None (normal).

1 = Mild (localized to a small region of the lid).

2 = Moderate (diffuse, most or all lid but not prominent/protruding).

3 = Severe (diffuse, most or all lid AND prominent/protruding).

4 = Very severe (diffuse AND prominent/protruding AND reversion of the lid).

Lashes

0 = Normal

1 = Abnormal (specify)

Conjunctiva - Erythema

0 = None (normal).

1 = Mild (a flush reddish color predominantly confined to the palpebral or bulbar conjunctiva).

2 = Moderate (more prominent red color of the palpebral or bulbar conjunctiva).

3 = Severe (definite redness of palpebral or bulbar conjunctiva).

Conjunctiva - Oedema

0 = None (normal).
1 = Mild (slight localized swelling).
2 = Moderate (moderate/medium localized swelling or mild diffuse swelling).
3 = Severe (severe diffuse swelling).
4 = Very severe (very prominent/protruding diffuse swelling).

Lens

0 = No opacification (normal lens).
1 = Mild lens opacification.
2 = Moderate lens opacification.
3 = Severe lens opacification.
N/A = Subject with artificial lens

Iris

0 = Normal
1 = Abnormal.

Anterior Chamber Inflammation (Slit beam = 0.3 mm wide, 1.0 mm long)

0 = None (no Tyndall effect).
1 = Mild (Tyndall effect barely discernible).
2 = Moderate (Tyndall beam in the anterior chamber is moderately intense).
3 = Severe (Tyndall beam in the anterior chamber is severely intense).

Cornea transparency

0= completely transparent
1= mild opacity
2= moderate opacity (iris details clearly visible)
3=severe opacity (iris details not clearly visible)
4=complete cornea opacity (anterior chamber structures not visible)

Cornea neovascularization

0= absence of neovascularization
1= neovascularization in less than 90°
2= neovascularization between 90° and 180°
3= neovascularization between 180° and 270°
4= neovascularization between 270° and 360°

Relevant findings of the SLE will be entered in the CRF.

4. ***Central corneal sensitivity by Cochet-Bonnet aesthesiometry:*** The Cochet-Bonnet aesthesiometer contains a thin, retractable, nylon monofilament that extends up to 6 cm in length. Variable pressure can be applied to the cornea by adjusting the monofilament length. The monofilament length ranges from 6 to 0.5 cm. As the monofilament length is decreased the pressure increases from 11 mm/gm to 200 mm/gm.

Corneal sensation will be measured in the affected eye(s) in the central area of the cornea using a Cochet Bonnet aesthesiometer before the instillation of any dilating or anesthetic eye drops.

Start the procedure by testing the corneal sensitivity within the area (center) of the PED or corneal ulcer of the affected eye.

Steps for using the Cochet Bonnet aesthesiometer:

- Extend the filament of the aesthesiometer to full length of 6 cm. Slowly advance the monofilament towards the eye until the tip perpendicularly touches the corneal surface.
Continue to exert a slight pressure until obtaining an inflection deviation of the filament of

about 4% (i.e. the first visible inflection). If a positive reaction to the touch of cornea is elicited proceed to step 3. If a positive reaction is not achieved proceed to step 2. (NOTE: A positive response is any action indicating corneal sensation whether communicated verbally or physically).

- b) Retract the filament incrementally in 0.5 cm and repeat this step until the patient gives a positive reaction indicating that the contact of the monofilament on the cornea has been sensed. (NOTE: The shorter filament lengths indicate decreased corneal sensation).
- c) Record the length of the filament in cm at which the patient sensed the contact with the cornea.
- d) Repeat steps 1-3 in each of the 4 corneal quadrants (superior nasal, inferior nasal, superior temporal and inferior temporal) outside the area of the PED or corneal ulcer in the affected eye and in each of the 4 corneal quadrants of the non-affected eye.
- e) To clean the instrument refer to your national standards for devices that contact the eye and tears or follow the suggested manufacturer's recommendations.

The length of the filament in cm at which the patient corneal sensation was observed for the tested area of the cornea will be entered into the eCRF.

5. ***Tear collection for Lubricin dosing:*** tear collection will be performed using tear wash technique with 40 µL of sterile saline solution. Dompé farmaceutici s.p.a. will be responsible for samples collection and dosing procedure. Samples will be shipped after LPLV

6. ***Tear Film Break Up Time (TFBUT):***

TFBUT will be measured by determining the time to tear break-up. The TFBUT will be performed after instillation of fluorescein solution into the inferior conjunctival cul-de-sac of each eye. The subject will be instructed to blink several times to thoroughly mix the fluorescein with the tear film. In order to achieve maximum fluorescence, the examiner should wait approximately 30 seconds after instillation before evaluating TFBUT. With the aid of a slit lamp at 10X magnification using cobalt blue illumination, the examiner will monitor the integrity of the tear film, noting the time it takes to form lacunae (clear spaces in the tear film) from the time that the eye is opened after the last blink. This measurement will be performed within 10 seconds maximum. The TFBUT will be measured twice during the first minute after the instillation of the fluorescein. If the 2 readings differ by more than 2 seconds a third reading is taken.

The TFBUT value will be the average of the 2 or 3 measurements.

Relevant TFBUT findings will be entered in the CRF.

7. ***Schirmer's test (ST) I (without anaesthesia):***

This test will be performed to measure aqueous tear secretion prior to the instillation of any dilating or anesthetic eye drops. Both eyes may be tested at the same time.

This test will be conducted in a dimly lit room. While the subject looks upwards, the lower lid will be drawn gently downwards and temporally. The rounded bent end of a sterile strip will be inserted into the lower conjunctival sac over the temporal one-third of the lower eyelid margin. The test should be done without touching directly the Schirmer test strip with the fingers to avoid contamination of skin oils. The subjects will be instructed to close their eyes gently.

After 5 minutes have elapsed, the Schirmer's test strip will be removed and the length of the tear absorption on the strip will be measured (millimeters/5 minutes).

The wetting distance at 5 minutes for each eye will be recorded in the CRF.

8. *Corneal fluorescein surface staining (Oxford score):*

The corneal fluorescein staining will be graded by using the Oxford scheme to assess cornea and conjunctiva epithelium damage. It will be performed after instillation of sodium fluorescein into the inferior conjunctival cul-de-sac of each eye with the aid of a slit lamp at 10X magnification using cobalt blue illumination.

Staining is represented by punctate dots on a series of panels (A-E). Staining ranges from 0-5 for each panel and 0-15 for the total exposed inter-palpebral conjunctiva and cornea. The dots are ordered on a log scale as follow:

Corneal fluorescein staining will be assessed after the Tear Film Break Up Time (TFBUT) examination and will also be graded according to the oxford scheme.

PANEL	GRADE	CRITERIA
A	0	Equal to or less than panel A
B	I	Equal to or less than panel B, greater than A
C	II	Equal to or less than panel C, greater than B
D	III	Equal to or less than panel D, greater than C
E	IV	Equal to or less than panel E, greater than D
>E	V	Greater than panel E

9. *Intraocular pressure (IOP):* IOP may be performed using either Goldmann applanation tonometry after the instillation of a topical anesthetic.

IOP should be measured in both eyes after completion of all other slit lamp examinations to avoid potential interference with the other evaluations. The subject and slit lamp should be adjusted so that the subject's head is firmly positioned on the chin rest and against the forehead rest without leaning forward or straining.

Both eyes will be tested, with the right eye preceding the left eye. The same equipment must be used throughout the course of the study.

IOP for each eye in mmHg will be recorded in the CRF.

6.4.1.2. *Tolerability and Safety*

Adverse Events

At each visit, after the subject has had the opportunity to spontaneously mention any problems, the Investigator or appropriate designee should inquire about AEs by asking the standard questions:

- “Have you had any health problems since your last study visit?”
- “Have there been any changes in the medicines you take since your last study visit?”

AEs should be reported for any clinically relevant change in concomitant medication(s) that is the result of an untoward (unfavorable and unintended) change in subject's medical conditions. Changes in any protocol-specific ocular or systemic parameter evaluated during the study are to be reviewed by the Investigator. In addition, the subject's responses to any questionnaire utilized during the study are to be reviewed by the Investigator. Any untoward (unfavorable and unintended) change in a protocol-specific parameter or questionnaire response that is clinically relevant is to be reported as an AE. These clinically relevant changes will be reported regardless of causality.

Visual analogue scale (VAS): Local ocular tolerability score: A global ocular discomfort score will be determined using a 100 mm VAS on which 0 means no symptoms and 100 means the worst possible discomfort. This evaluation is to be performed before any ophthalmic assessment at a given study visit. Specific ocular symptoms to be assessed with the VAS include:

- dryness
- foreign body sensation,
- burning/stinging,
- itching,
- pain,
- sticky feeling
- blurred vision
- photophobia

VAS parameters that will be used for the evaluation of tolerability and safety are: .

The subjects will be instructed to place a vertical mark on the horizontal line indicating his/her level of discomfort for that symptom in the eyes. The VAS is expected to take the subject about 5 minutes to complete. A VAS is a measurement instrument that tries to measure a characteristic or attitude that is believed to range across a continuum of values and cannot easily be directly measured.

